### ***Pediatric Evidence***

A recent guideline was published by The Pediatric Oncology Group of Ontario (POGO) Mucositis Prevention Guideline Development Group specific to PBM. After review of the literature, the group placed high value on the possible reduction in mucositis with such intervention with a low risk of harm. While the evidence was adequate for potential benefit, the recommendation was weak due to the need for specialized equipment, expertise and unknown feasibility to deliver the therapy in routine clinical care.[13] This recommendation was taken from a systematic review by Oberoi et al, [14] of 18 prophylactic PBM studies. The meta-analysis reported PBM significantly reduced the incidence of severe mucositis, overall grade of oral mucositis, the incidence of severe pain, overall mean pain scores and use of opioid analgesia.

PBM has been evaluated in two small sample studies, as a device to prevent oral mucositis in pediatric patients undergoing HCT.[6, 15] The first study treated 9 patients with PBM directly to the mucositis lesion and 12 control who had received a HCT or chemotherapy. The patients were treated for 5 days. Patients were evaluated by mucositis duration, with PBM OM duration  $5.8 \pm 2$  days and the control  $8.9 \pm 2.4$  days. [15] The second study treated 12 patients four times a week with a protocol of combined intraoral and extraoral PBM for an average of 22 days and matched to a retrospective group. Mucositis severity was significantly less than the control group, and higher (non-significant) oral function than the control. [6] Another study reviewed 51 HCT pediatric patients treated with daily PBM and found good clinical outcomes with control of mucositis severity and pain reduction.[16] This technique was further evaluated with the objective of controlling pain associated with oral mucositis in a pediatric transplant population with successful outcomes.[17]

Many of the cited studies have delivered PBM intraoral as individual small “spots” via a laser probe, specific to oral mucositis sites from the lips to soft palate in a time consuming manner and one which may be challenging in pediatric use.[18] A more recent approach is use of a larger light-emitting diode (LED) through an extra oral approach, treating the oral, oropharyngeal, and esophageal mucosa, with improved patient corporation. [19] A recent study evaluated the feasibility of extraoral PBM by trained nurses for the prevention of oral mucositis in HCT patients.[20] The study enrolled 13 HCT patients 4 years and older. The study did not evaluate

efficacy but found the treatment delivery to feasible and well tolerated.

The timing of PBM during therapy is inconsistent across studies. An adult study began treatment at day 1 of conditioning and continued until day 2 post progenitor cell infusion.[7] Three pediatric studies were reviewed for initiation of PBM, with two studies beginning PBM at day 1 of conditioning, [6, 20] and the third study initiating PBM after the completion of conditioning.[16] Two studies continued PBM until engraftment[6, 16] and the third continued until day 20 after cell infusion.[20]

### ***HCT Patient Experience at St. Jude***

To better understand our patient experience, we conducted a retrospective review of the HCT patient experience and reviewed the medical records of 45 patients. [21] Patients were divided into two groups based on mucositis severity (mucositis defined as  $\geq$  grade 3 on the Common Terminology Criteria of Adverse Events). Demographic and clinical data were obtained via electronic medical record review and compared between groups.

This retrospective study reviewed transplant admissions between June 2015 and May 2016.[21] During this period, 75% of the allogenic transplant patients had  $\geq$  grade 3 mucositis with median mucositis onset at Day 3 (range -3 to 9) after progenitor cell infusion, median mucositis duration of 11 days, median of 9 days from (range 3 to 26) mucositis onset to engraftment and a median of 2 days (range -21 to 26) from engraftment to the end of mucositis. All of the 25 patients received parenteral nutrition and 96% received pain medications for oral pain. Patients with  $\geq$  grade 3 mucositis were more likely than those with grade 1/2 mucositis to have positive blood or oral cultures ( $p=0.018$ ), to have undergone an allogeneic transplant [ 17 of 21 patients ( $p=0.008$ )] and had significantly longer hospitalizations ( $p=0.002$ ). However, our review did find a subset of patients receiving auto transplant, such as neuroblastoma, to be at risk for high grade mucositis.

Our retrospective data revealed the onset of mucositis can be as early as Day -3 with continuation until engraftment. While studies have variability in timing of PBM, these findings support our proposed initiation of therapy to begin on the first morning of conditioning until engraftment with an ANC  $\geq 500$  for two consecutive days. Seventy-five percent of the those with grade 3 mucositis had undergone an allogenic transplant and 33% autologous. Therefore, patients undergoing autologous transplant and at risk for grade 3 mucositis, as identified by the bone marrow transplant clinicians will be included in the exploratory objective.

To determine sample size, we extended our review of allogenic transplant recipients from May 2015 to June 2019. Our review identified 93 first allogeneic transplant patients, with 66 (71%) developing grade 3 mucositis during transplant.

### **Play-Based Procedural Preparation**

Child life specialists are psychosocial providers who focus on improving coping skills and reducing stress among children and families in medical environments. These developmental experts implement play-based interventions to promote feelings of control, familiarity, understanding, and predictability in otherwise stressful and unfamiliar hospital settings. One such intervention is play-based preparation, in which child life specialists use age appropriate language and medical play to assess children's and families' understanding, to teach new concepts, and to determine coping plans that are implemented during procedures (Burns-Nader & Hernandez-Reif, 2016). This style of preparation incorporates a familiar concept, play, with unfamiliar medical concepts and materials to increase predictability, understanding, and expectations to assist children and families' abilities to cope with their hospitalization.[22]

Child life interventions are useful for preparing children in developmentally appropriate ways, and they also have an impact on parental satisfaction associated with medical experiences. When child life specialists provide psychosocial services prior to and during children's procedures, parents are more satisfied with their child's care and find the child to be more cooperative (Sanchez Cristal, et. al., 2018). Parents also report a strong appreciation for the respect and compassion associated with interventions supported by child life specialists.

Preparing children and families for procedures reduces preprocedural anxiety and improves postprocedural emotions of children and families. [23] Although several studies demonstrate the positive impact of child life preparation on children's responses to invasive procedures such as needle sticks and surgeries less is known about the role of play-based preparation for non-invasive procedures. These non-invasive procedures, such as routine physical examinations of blood pressure or temperature, can also be unfamiliar and scary for children in the hospital. Low-level light therapy (LLLT) for mucositis is a non-invasive and unfamiliar intervention for children. Using play to prepare children for this procedure may help clarify its importance and their role while also creating space to develop a coping plan. The following child life aims will explore the impact of a play-based preparation for LLLT on parent satisfaction and feasibility of patient participation.

### **3.0 RESEARCH PARTICIPANT ELIGIBILITY CRITERIA AND STUDY ENROLLMENT**

According to institutional and NIH policy, the study will accession research participants regardless of gender and ethnic background. Institutional experience confirms broad representation in this regard.

#### **3.1 Inclusion Criteria**

- 3.1.1 No age limitation
- 3.1.2 To be admitted for an allogeneic hematopoietic cell transplant,
- 3.1.3 All eligible autologous hematopoietic cell transplant, at risk for grade 3 mucositis per transplant service secondary to conditioning regimen or previous history of grade 3 mucositis
- 3.1.4 Dental exam prior to admission, as per preadmission criteria
- 3.1.5 Willingness of research participant to provide assent/consent and parent/ legal guardian/representative to give written informed consent.

#### **3.2 Exclusion Criteria**

- 3.2.1 Deemed by transplant team as unable to participate
- 3.2.2 Known sensitivity to light therapy
- 3.2.3 Inability or unwillingness of research participant or legal guardian/representative to give written informed consent.
- 3.2.4 CAR-Tcell Protocol

#### **3.3 Research Participant Recruitment and Screening**

Potential participants undergoing HCT will be identified in the weekly bone marrow pre-admission conference. Each participant being admitted for an allogenic transplant and meeting inclusion criteria will be offered PBM therapy. The bone marrow transplant clinicians may identify autologous recipient at risk for grade 3 mucositis per conditioning regimen or history of high-grade mucositis. These participants will be included for the exploratory objective. For all patients meeting inclusion criteria, an appointment will be made with the participant and family during the HCT evaluation period. The potential participant and parents will be approached by a member of the study team who will briefly explain the

study and respond to any patient/family questions. An educational slide show presentation delivered by an ipad will describe the PBM process and mechanism (see attached). At that time, the patient and parents will be asked if they wish to participate in the study. If they agree, the informed consent/assent document will be reviewed and signed. This meeting will take place approximately one week to day of admission to in-patient Transplant Service. All patients who meet the study criteria will be approached for enrollment.

After low level light therapy consent, participants will be offered the opportunity to receive a play-based preparation by a certified child life specialist (CCLS). Those who elect to receive this child life preparation will be scheduled to meet with a trained CCLS prior to admission. The play-based preparation will incorporate age and developmentally appropriate explanations of the non-invasive procedure and will be adapted to each patient's psychosocial and cognitive developmental needs. To standardize the child life preparation, the following components will be included in each of the interventions: hands on manipulation of the LLLT equipment (ie. Glasses and light tool), demonstration and return demonstration of procedure on a medical doll, and discussion and development of coping plan for procedure. The play-based preparation intervention will last approximately 30 minutes.

### 3.4 Enrollment on Study at St. Jude

A member of the study team will confirm potential participant eligibility as defined in Section 3.1-3.2, complete and sign the 'Participant Eligibility Checklist'. The Study Team will enter the Eligibility Checklist information into the Central enrollment system. Eligibility will be reviewed, and a research participant-specific consent form and assent document (where applicable) will be generated. The signed consent/assent form must be faxed or emailed to the Clinical Trials Operations (CTO) [REDACTED] or emailed to [REDACTED] in order to complete the enrollment. If you have a prospective research enrollment and need assistance releasing your consent on a weekend or holiday, please call the Milli helpline ([REDACTED]).

### 3.5 Procedures for Study Staff

Prior to initiating the study, nursing research staff attended a photobiomodulation therapy workshop, under the direction of the Thor laser manufacture. All staff have been trained and assessed in extraoral PBM application during the workshop. Additionally, the protocol has been written in consultation with [name], who has been instrumental in the study of PBM for the prevention of

St. Jude Children's Research Hospital  
IRB NUMBER: 19-0225  
IRB APPROVAL DATE: 01/28/2021

mucositis in adults and was co-author of the international mucositis guidelines published in *Supportive Care in Cancer*.[24] Light therapy is commonly administered by dental technicians and a small (n=13) feasibility study found that trained staff (nursing) were adequate in administration of PBM. [20] Study staff will also be trained in consent processes, data transfer, and plans to monitor intervention integrity and data quality.

## 4. DESIGN AND METHODS

### 4.1 Design and Study Overview

This study will enroll children and adolescents prior to admission for an allogeneic HCT, and those undergoing an autologous transplant at deemed at risk for grade 3 oral mucositis. Light therapy will be administered by trained persons within Nursing Research Division: [name], [name], [name] and [name]. The parent may hold the device in place with assistance from the trained persons. Patients will receive extra-oral and intra-oral PBM on the first day of conditioning, those undergoing an allogeneic HCT will have treatment daily until engraftment or +Day 20 (event occurring first). For those undergoing an autologous transplant treatment will continue until engraftment or until the patient is without mucositis for two consecutive days. If the patient becomes acutely ill during therapy and misses 4 consecutive days of PBM, the data will not be evaluated. These patients will be replaced to give 66 evaluable patients for the primary objective. Patients in isolation will continue to receive PBM with the device covered in plastic and cleaned prior to leaving the isolation holding area.

The PBM will be delivered through application of the LED Cluster Probe externally to the right external buccal, left external buccal, mid face with mouth open and submandibular and left/right cervical. Patients who develop an oral lesion, intra-oral directed therapy will be administered with the dental light probe. For patients that can tolerate, an intraoral probe will deliver light directly onto the oral mucosa, this will then replace the mid face application with mouth open. Each laser application will be timed at 60 seconds. [8] The PBM treatment will be administered via the THOR Model LX2M unit. All participants will receive the standard mouth care regimen prescribed for HCT patients. Observation and treatment will begin the first day of conditioning and continue daily until engraftment (2 consecutive days of ANC  $\geq$  500) or Day +20 (which comes first) and until mucositis resolution for two consecutive days for the autologous transplant.

Feasibility will be assessed similar to Treister et al [20] through the number of successful treatments administered by the total number of attempted treatments, providing the percentage of successful treatment administered. Daily treatment will include 6 sites of PBM application, with application documented as receiving all 6 applications, in part treatment (at least one to five sites) or no treatment. A successful treatment is defined as the treatment is successfully administered to 4 or more sites. Reasons for partial or no treatment will be documented. Criteria for feasibility is that the percentage of successful treatments administered exceeds 75%. The collected data will be summarized for total days on protocol, days treatment is received, cumulative dose and the number of treatments received at each site.

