## 6.3 Off-Study Evaluations

1. Patients are off-study on last day (Day +20 or engraftment or absence of mucositis)

of PBM administration except for patients undergoing autologous tandem transplant will discontinue treatment with mucositis resolution and then resume light therapy with second transplant. Thus, these patients will remain on study until resolution of mucositis after second transplant. Therefore, will not reconsent with the second transplant, parents and patient may refuse if desired

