## **7. CRITERIA FOR REMOVAL FROM PROTOCOL THERAPY AND OFF-STUDY CRITERIA**

### **7.1 Off-study criteria**

#### **7.1.1 Death**

#### **7.1.2 Request of the Patient/Parent**

#### **7.1.3 Discretion of the Study PI, such as the following**

- The researcher decides that continuing in the study would be harmful
- A treatment is needed that is not allowed on this study
- The participant misses > 3 consecutive days of PBM the data cannot be used in the study
- The participant's condition gets worse
- New information is learned that a better treatment is available, or that the study is not in the participant's best interest
- Study evaluations are complete

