# 10. STATISTICAL CONSIDERATIONS

## 10.1 Sample Size

A review from June 2015 to May 2019, identified 93 first allogeneic transplant patients with similar conditions, and 66 (71%) of them developed grade 3 or above oral mucositis. With an estimated clinically meaningful effect size of 20% for PBM, the estimated percentage of patients who will receive PBM and develop grade 3 oral mucositis is 51%.

St. Jude Children's Research Hospital  
IRB NUMBER: 19-0225  
IRB APPROVAL DATE: 01/28/2021

We will use the two-stage one-arm design with historical controls to monitor both efficacy and futility. The complete historical control sample will be used in both the interim analysis and final analysis. The test statistic in Chang et al [28] treats the historical control sample as if they are the control arm in a two-arm design. Given the relatively small sample size, we did not use the asymptotic distribution of the test statistic. Instead, we used Monte Carlo methods to estimate the sampling distribution of the test statistic under null and alternative hypotheses by 100,000 Monte Carlo data sets. The simulation program is written in R.

The rules of which accommodate both efficacy and futility. The null hypothesis is  $p_0=0.71$ ; the alternative hypothesis is  $p_1=0.51$ ; The type-I error rate = 0.05 and power 0.8 are used.. The detailed information about the two-stage design is shown in the following table. The attained type-I error rate and power are 0.048 and 0.813, respectively.

Loo k #	n	Boundari es		Boundary Crossing Probability (Incremental)			
				Under H0		Under H1	
		Efficac y	Futilit y	Efficac y	Futilit y	Efficac y	Futilit y
1	40	20	29	0.015	0.508	0.526	0.015
2	66	38	39	0.033	0.444	0.288	0.172
Total				0.048	0.952	0.813	0.187

The expected sample size under null and alternative hypotheses is 56 and 51, respectively. In the historical data between July 2015 and May 2016, 24 patients received allogeneic HCT. We estimate that study accrual of 66 transplant patients will be completed in 31 months after study activation.

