## 10.2 Statistical Analyses

### 10.2.1 Statistical analysis for the primary objective

*To evaluate the feasibility and efficacy of photobiomodulation therapy (PBM) in reducing oral mucositis in children and adolescents at risk for grade 3 oral mucositis undergoing an allogeneic hematopoietic cell transplant (HCT).*

Hypothesis 1: Children and adolescents will receive 75% of the attempted PMB treatment and will be less likely to develop grade 3 oral mucositis from the 1st day of conditioning to day +20 of transplant or engraftment.

Descriptive statistics (counts, percentages, mean, median, standard deviation and interquartile range) and confidence interval will be calculated for the percentage of successful treatment administered, total days on the protocol, days treatment is received, cumulative dose and the number of treatments received at each site.

The count, percentage and confidence interval will be calculated for allogeneic HCT patients who receive PBM and develop Grade 3 mucositis. Whether the percentage of the prospective sample is significantly different from the historical rate is accessed by the monitoring rule in Section 10.1.

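### Patients with long gaps in PBM are removed from the primary efficacy data, the historical sample has no comparable exclusion, and no analysis of all patients who started PBM is planned

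*Combined protocol and SAP*

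**What the plan says.** Two sections of the combined protocol and SAP remove patients from the data for missed PBM.

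- Section 4.1: "If the patient becomes acutely ill during therapy and misses 4 consecutive days of PBM, the data will not be evaluated". It continues: "These patients will be replaced to give 66 evaluable patients for the primary objective".
- Section 7.1.3: "The participant misses > 3 consecutive days of PBM the data cannot be used in the study". This item is listed beneath "Discretion of the Study PI, such as the following". It does not require acute illness and does not mention replacement.

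Neither section makes an exception for a patient whose grade 3 mucositis is already charted.

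The comparator is described in Section 10.1: 93 first allogeneic transplants with similar conditions, of whom 66 (71%) had grade 3 or higher mucositis. "The complete historical control sample will be used in both the interim analysis and final analysis". For the two-stage design (40, then 66 patients) the plan reports: "The attained type-I error rate and power are 0.048 and 0.813, respectively".

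Section 10.2.1 describes the primary efficacy summary: "The count, percentage and confidence interval will be calculated for allogeneic HCT patients who receive PBM and develop Grade 3 mucositis". It refers the decision to the Section 10.1 rule. It does not mention the exclusion, and it defines neither an all-starters analysis nor a sensitivity analysis for replaced patients.

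**The concern.** Whether a patient counts in the primary efficacy set depends on what happens after PBM starts. Nothing comparable is applied to the historical 93, although the design treats them as a control arm. If the excluded patients differ from the rest in their risk of grade 3 mucositis, the evaluable rate no longer estimates the rate among all patients who started, and the comparison with 66/93 is no longer like with like.

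If grade 3 mucositis is more common among the excluded, PBM looks better than it is and the chance of wrongly declaring efficacy exceeds the stated 0.048. If it is less common, the bias reverses and a real benefit may be missed. With no all-starters result, the report could not show whether its conclusion depends on who was replaced.

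**Working it through.** **Inputs from Section 10.1.** Null rate 0.71; alternative 0.51; looks at 40 and 66 patients; efficacy at 20 or fewer and futility at 29 or more at look 1; efficacy at 38 or fewer at look 2; historical sample of 93.

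**Inputs that are assumptions.** The share of starters excluded (e) and the grade 3 rate among them (r). The documents give neither, so a range is shown.

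**Step 1: reproduce the plan's figures.** The rule was enumerated exactly, with the historical count as Binomial(93, 0.71) and a pooled z statistic. The plan does not print its critical values, so they were fitted inside the ranges that the printed counts imply against 66/93:

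| Boundary | z at the adjacent counts | Fitted cutoff |
|---|---|---|
| Look 1 efficacy | 20/40: -2.320; 21/40: -2.053 | z ≤ -2.173 |
| Look 1 futility | 28/40: -0.112; 29/40: 0.179 | z ≥ 0.00 |
| Look 2 efficacy | 38/66: -1.749; 39/66: -1.558 | z ≤ -1.72 |

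Result: type I error 0.0480 and power 0.812, against the stated 0.048 and 0.813. The totals match. The split under the null is 0.018 + 0.030, against the printed 0.015 + 0.033. A second fit, closer to the printed increments, gives 0.0472 and 0.8113.

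**Step 2: null rate in the evaluable set.** If PBM has no effect and all starters have rate 0.71, the evaluable rate is (0.71 − e × r) / (1 − e). For example:

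- 5% excluded, 80% grade 3: (0.71 − 0.040) / 0.95 = 0.7053
- 10% excluded, 90% grade 3: (0.71 − 0.090) / 0.90 = 0.6889
- 10% excluded, 60% grade 3: (0.71 − 0.060) / 0.90 = 0.7222

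**Step 3: put these rates through the rule, leaving the historical sample at 0.71.**

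| Excluded (e) | Grade 3 among excluded (r) | Evaluable rate | Chance of declaring efficacy with no PBM effect |
|---|---|---|---|
| none, or any share | 71% | 0.7100 | 0.048 |
| 2% | 80% | 0.7082 | 0.051 |
| 5% | 80% | 0.7053 | 0.055 |
| 5% | 90% | 0.7000 | 0.063 |
| 10% | 90% | 0.6889 | 0.084 |
| 5% | 60% | 0.7158 | 0.041 |
| 10% | 60% | 0.7222 | 0.034 |

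The second fit gives 0.054 (5%, 80%), 0.082 (10%, 90%) and 0.033 (10%, 60%), so the pattern does not depend on the choice of cutoffs.

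**Step 4: power if all starters became the primary set.** Keep 66 patients and the same cutoffs, and suppose a share e gets no benefit (rate 0.71). The overall rate is (1 − e) × 0.51 + e × 0.71.

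- e = 5%: 0.4845 + 0.0355 = 0.520, power 0.78
- e = 10%: 0.459 + 0.071 = 0.530, power 0.74

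**The case against.** **The evaluable set is a legitimate choice.** A pre-specified evaluable set with replacement is common in a small single-arm study that asks about PBM as delivered, and making all starters primary would change the question and cost power. This stands. It is a reason to keep the evaluable analysis, but not to omit the other one.

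**The effect may be small.** At low exclusion rates the type I error barely leaves its nominal level, and nothing in the documents supports a 90% grade 3 rate among the excluded. This stands too, and it limits the claim to a possible bias of unknown size.

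**Section 10.2.1 could already mean all treated patients.** It speaks of patients who receive PBM. But Sections 4.1 and 7.1.3 bar use of the excluded data, and Section 4.1 ties the 66 to evaluable patients. At best the primary population is ambiguous.

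Four stronger readings are tempting but not supported:

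- *The bias favours PBM.* Section 2.2 links grade 3 or higher mucositis with positive cultures and longer stay, which makes that direction plausible. It does not describe who misses PBM, so the direction is not shown.
- *The historical sample is wholly unfiltered.* It is limited to first allogeneic transplants with similar conditions. What it lacks is an exclusion for illness or interrupted care.
- *Section 6.3 cuts off outcome collection early.* It says "Patients are off-study on last day (Day +20 or engraftment or absence of mucositis". The first two of these end the allogeneic efficacy window anyway, and Section 4.1 links the third to autologous patients. Any gap comes from removal under Section 7.1.
- *One replaced patient can reverse the result, because 38 is efficacy and 39 is futility.* Any final look has adjacent boundaries, so this does not show bias.

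**Conclusion.** The point holds and should be fixed. Followed as written, the plan selects patients after treatment start in the PBM group only, compares them with a sample that is not selected in that way, and provides no analysis that would reveal the consequence.

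That the rule exists and that no all-starters analysis is planned are certain from the text. The size and direction of any bias are not. Over the assumed range of 2% to 10% excluded and 60% to 90% of them with grade 3 mucositis, the chance of declaring efficacy with no PBM effect runs from about 0.034 to 0.084 against the stated 0.048. It does not change if the excluded have the same 71% rate.

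Sections 4.1 and 7.1.3 also disagree. One is a fixed rule tied to acute illness, with replacement. The other covers any reason, sits under investigator discretion and is silent on replacement. The excluded group is therefore not uniquely defined.

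No claim is made about the feasibility result or the sample size.

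**What to change.** Change the data-use wording only. PBM delivery and the clinical reasons for stopping stay as they are.

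1. In Section 10.2.1, pre-specify an analysis of every allogeneic patient who starts PBM. Count grade 3 or higher mucositis charted in routine care through Day +20 or engraftment, whichever is first, regardless of missed PBM. At both looks, report its rate, confidence interval and the same comparison with 66/93 beside the evaluable result. Use the test statistic for this, since the printed counts apply only at 40 and 66 patients. If the two analyses disagree, say so in the conclusion.
2. In Section 7.1, state that chart abstraction of mucositis grade continues, within consent, to the end of that window for patients taken off for missed PBM. Section 4.1 already has mucositis observed by non-study staff as part of clinical care, so the grades should exist.
3. Report the number excluded and the number replaced, with reasons and grade 3 status.
4. Reconcile Sections 4.1 and 7.1.3 on the reason (acute illness or any), on fixed rule or discretion, and on replacement.

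The cost is protocol and SAP wording plus minor abstraction, and the all-starters rate may be less favourable. Making all starters the primary set is an option but is not required. If the sponsor chooses it, the stated power should be revised, for example to 0.78 or 0.74 if 5% or 10% of starters get no benefit.

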### 1.1 Primary Objective

*To evaluate feasibility and efficacy of photobiomodulation therapy (PBM) in reducing oral mucositis in children and adolescents at risk for grade 3 oral mucositis undergoing an allogeneic hematopoietic cell transplant (HCT).*

Hypothesis 1: Children and adolescents will receive 75% of the attempted PMB treatment and will be less likely to develop grade 3 oral mucositis from the 1st day of conditioning to day +20 transplant or engraftment (event occurring first)

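### The missed-days exclusion is not confined to efficacy, so as written it also drops and replaces patients in the feasibility measure and can overstate the share of successful treatments

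*Combined protocol and SAP*

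**What the plan says.** Section 1.1 sets one primary objective with two parts: "To evaluate feasibility and efficacy of photobiomodulation therapy (PBM) in reducing oral mucositis". Section 10.2.1 repeats it.

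Section 4.1 defines feasibility "through the number of successful treatments administered by the total number of attempted treatments". It adds: "A successful treatment is defined as the treatment is successfully administered to 4 or more sites", out of six sites a day. The threshold is: "Criteria for feasibility is that the percentage of successful treatments administered exceeds 75" per cent. Days are documented as full, partial or no treatment, and "Reasons for partial or no treatment will be documented". The word *attempted* is not defined.

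The exclusion appears twice:

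- Section 4.1: "If the patient becomes acutely ill during therapy and misses 4 consecutive days of PBM, the data will not be evaluated". The next sentence reads: "These patients will be replaced to give 66 evaluable patients for the primary objective".
- Section 7.1.3, among examples of off-study reasons at the PI's discretion: "The participant misses > 3 consecutive days of PBM the data cannot be used in the study".

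In whole days the two thresholds are the same (more than 3 is 4 or more). The conditions differ: 4.1 requires acute illness, while 7.1.3 does not but is discretionary.

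Section 10.2.1 plans descriptive statistics and a confidence interval for the percentage of successful treatments. Neither it nor 4.1 names a population for feasibility, such as all patients who started PBM.

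**The concern.** Feasibility asks whether PBM can be delivered. The exclusion is triggered, at least in part, by PBM not being delivered. If the data of these patients may not be used, all their sessions leave both the numerator and the denominator. Replacement then restores the count to 66, and the plan does not ask for the number replaced to be reported beside the feasibility percentage.

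Leaving out patients after a long gap can be argued for an efficacy question about treatment as delivered. It is hard to defend for the question of whether delivery succeeds.

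The stake is practical. Section 2.2 reports that a pediatric guideline gave only a weak recommendation, partly because feasibility in routine care was unknown, and section 1.0 states the aim of bringing PBM into nursing guidelines. Acutely ill transplant patients are among those in whom feasibility is least certain. The delivery summaries by play-based preparation in 10.2.3 use the same measures and would be affected in the same way.

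**Working it through.** **1. The plan's own figure.** The documents give no calculation for the 75% criterion. The only design calculation is the two-stage efficacy design in 10.1 (looks at 40 and 66 patients, 93 historical controls, 0.71 against 0.51, attained type I error 0.048 and power 0.813). Simulating a pooled two-proportion Z statistic with the historical patients as a random control arm gives power 0.80 to 0.825 and type I error 0.043 to 0.054. The spread arises because the cut-offs on the Z scale are not stated. The power reproduces, and nothing in that calculation depends on the feasibility population.

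**2. Inputs for feasibility.** From the documents: 66 evaluable patients, a 75% threshold, and at least 4 consecutive missed days in each excluded patient. Assumed, because the documents do not give them: T = 28 scheduled days; k excluded and replaced patients; s = 80% success in retained patients and on the excluded patients' other days; g missed days per excluded patient.

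**3. Ceiling for an excluded patient.** Delivery against schedule is at most (T − 4)/T: 20/24 = 83.3%, 24/28 = 85.7%, 27/31 = 87.1%, before any other failure.

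**4. If gap days count as attempted.** The percentage in all starters is [66·T·s + k·(T − g)·s] / [(66 + k)·T]. For k = 7 and g = 4: (1478.4 + 134.4)/2044 = 78.9%. The plan as written would report 80% in every cell below.

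| Excluded, k (share of starters) | g = 4 | g = 14 | g = 20 |
|---|---|---|---|
| 7 (10%) | 78.9% | 76.2% | 74.5% |
| 12 (15%) | 78.2% | 73.8% | 71.2% |
| 17 (20%) | 77.7% | 71.8% | 68.3% |

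The overstatement runs from 80 − 78.9 = 1.1 points to 80 − 68.3 = 11.7 points. Five of the nine cells fall below 75%. With s = 85% and k = 17 the figures are 82.5%, 76.3% and 72.6%, so only the last falls below.

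**5. If gap days do not count as attempted.** The formula becomes [66·T·s + k·(T − g)·s] / [66·T + k·(T − g)] = s. The result stays at 80% whatever k and g are. Exclusion then moves the percentage only if the excluded patients' other sessions succeed at a different rate.

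**6. Break-even.** With equal sessions per patient, 80% in retained patients and success q in excluded ones, the all-starters figure equals 75% at an excluded share of (0.80 − 0.75)/(0.80 − q). This is 8.3%, 12.5%, 16.7% and 25% for q = 20%, 40%, 50% and 60%. At q = 40%, 9 excluded beside 66 retained give (52.8 + 3.6)/75 = 75.2%, and 10 give (52.8 + 4.0)/76 = 74.7%.

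**7. When counting stops.** Section 7.1 makes the gap an off-study reason, so this matters. Take off-study on day 14 after a 4-day gap, with gap days counted as failures:

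- 66 at 80%, 10 excluded: counted to off-study, (1478.4 + 80)/(1848 + 140) = 78.4%; counted to the due end, 1558.4/2128 = 73.2%.
- 66 at 78%, 7 excluded: counted to off-study, (1441.4 + 54.6)/(1848 + 98) = 76.9%; counted to the due end, 1496.0/2044 = 73.2%.

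The same patients meet or miss the criterion depending on a counting rule that the plan does not state.

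**The case against.** The strongest reply is that feasibility is a ratio of successes to attempts. If a day missed through acute illness is not an attempt, it was never in the ratio, and dropping these patients barely changes it (step 5). This stands as a limit on size and direction. It does not remove the problem: on that reading the percentage ignores missed days for everyone, and the recorded no-treatment category in 4.1 suggests that the other reading is at least as natural.

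Second, the rule in 4.1 applies only with acute illness. Under it, a child who refuses or cannot tolerate PBM stays in. The unconditional rule in 7.1.3 is discretionary. A reader might infer that the 75% criterion is judged only in children who never had a 4-day gap. The documents do not support that: 4.1 does not say it, and 7.1.3 allows it without requiring it.

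Third, feasibility is analysed descriptively, the formal rule in 10.1 concerns mucositis only, and section 4.1 tabulates days on protocol and days treated by case. This is true, but 4.1 still sets a pass mark, and the plan does not say whether excluded cases appear in that table.

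Fourth, counting against scheduled days is a different quantity from success per attempt, and the treatment log in 6.2 may stop when a patient goes off study. Both points are fair. They argue for reporting both quantities and for deriving due days from the engraftment date or Day +20. They do not argue for leaving these patients out.

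**Conclusion.** The point holds as a defect in how the feasibility population is defined. Read literally, 4.1 and 7.1.3 apply the exclusion to the whole primary objective, so a measure of delivery is conditioned on delivery and the losses are refilled by replacement.

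Its size is not known. Under the assumptions in the working, the overstatement lies between about zero (gap days not attempts, similar success on other days) and about 12 points (gap days counted, 20% of starters excluded, 20 of 28 days missed). The documents give no exclusion rate, course length or success rate for excluded patients.

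A reader might go further and conclude that delivery will be overstated, or that the criterion will be met only because failures were removed. The documents do not support either. The 75% verdict changes only in part of the assumed range, and with a simple 4-day gap and 80% success elsewhere it does not change at any exclusion share tabulated. The plan should still be settled before the percentage is known, because the undefined terms alone can decide the result.

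**What to change.** - State in 4.1, 7.1 and 10.2.1 that the missed-days exclusion does not apply to feasibility.
- Compute feasibility over every allogeneic patient who started PBM, including those later replaced.
- Define *attempted*. Report success per attempted treatment and, beside it, success per scheduled treatment day through the day PBM was due to end, with gap days counted as not successful.
- Name in advance which of the two is judged against 75%.
- Report the number of patients replaced, with reasons, next to that result.
- Reconcile the wording of 4.1 and 7.1.3 on the illness condition and on PI discretion.

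The cost is wording in three sections and, for patients taken off study, a count of due days from the engraftment date (already abstracted under 6.2) or Day +20. The feasibility percentage may come out somewhat lower. The efficacy sample size of 66, the boundaries and the power of 0.813 do not change.
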